Then, participants are asked if they were familiar with the names of any intervention trainer involved in the study. Finally, they are thanked for their participation and informed about the next steps. After completing the baseline assessment, they are randomly assigned to either the waitlist or the intervention condition by simple randomization using a true random number

generator ([random.org](https://www.random.org)). Participants in the intervention condition are contacted by a trainer that would then conduct the intervention session with them in either Dutch, English, or German. Participants in the intervention condition followed six 1-hour online sessions of a meaning-centered intervention for internalizing symptoms (for details on the original intervention designed for eating disorders, see van Doornik et al., 2024), with sessions taking place approximately every 4 days. Immediately after completion of the last intervention session, participants in the intervention condition will receive the link to the post-assessment questionnaire. Participants in the waitlist condition will be informed that they are assigned to the waitlist condition and that in a month from now they will receive the link to the post-assessment. Waitlist participants will be also informed that they can follow the intervention themselves once data collection completes, prospectively in June 2026. One month after the post-assessment, both conditions will be asked to complete the follow-up assessment. For all assessments, participants will be compensated with SONA credits.

Statistical Analyses

All analyses will be run in R. All analyses will be run as completer analysis, given our aim to assess the efficacy of the present intervention in a subclinical sample (Silverman et al., 2024). Missing values will be imputed using predictive mean matching. Analyses will be run with and without influential observations (i.e., observations showing high standardized residuals and/or leverage). Differences in outcomes between analyses with and without influential points will be reported.

A minimal sample size of $N=128$ is required to yield power of 0.8 based on testing a one-way ANCOVA with α -level of .05, effect size of $f=0.25$, number of groups = 2, max. number of covariates = 2, and numerator $df=1$. We aimed to recruit 142 participants, assuming a drop-out rate of 10%.

Primary Outcomes: Meaning in life and Internalizing Symptoms

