H1a: The meaning-centered intervention increases meaning in life at post assessment and follow-up, compared to a waitlist control.

H1b: The meaning-centered intervention reduces internalizing symptoms at post assessment and follow-up, compared to a waitlist control.

The effect of the intervention on both meaning and internalizing symptoms will be tested by running a MANCOVA with post-assessment sum score of presence subscale of the MLQ and DASS-21 sum score as dependent variables, with baseline presence sum score and baseline DASS-21 sum score as covariate and condition (intervention, waitlist) as the between-subjects factor. This step will be repeated with the follow-up scores as dependent variables and baseline and post-assessment score as covariates. All resulting p values will be tested against an alpha level of 0.05.

The effect of the intervention specifically on either primary outcome will be tested using ANCOVAs. The first ANCOVA will test the effect on meaning in life, with post-assessment sum score of presence subscale of the MLQ as dependent variable and baseline presence sum score as

covariate, with condition (intervention, waitlist) as a between-subjects factor. This step will be repeated with the follow-up scores as dependent variable and baseline and post-assessment score as covariates.

The effect of the intervention on internalizing symptoms will be tested by an ANCOVA with post-assessment DASS-21 sum score as dependent variable and baseline DASS-21 sum score as covariate, with condition (intervention, waitlist) as a between-subjects factor. This step will be repeated with the follow-up scores as dependent variable and baseline and post-assessment score as covariates.

Secondary Outcomes: Dyscontrolled Drinking and Three-Dimensional Meaning

H2a: The meaning-centered intervention reduces dyscontrolled drinking at post assessment and follow-up, compared to a waitlist control.

H2a: The meaning-centered intervention increases coherence, purpose, and significance at post assessment and follow-up, compared to a waitlist control.

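### The two post-assessment primary ANCOVAs adjust only for their own baseline, although the MANCOVA at the same visit uses both baselines; adding the other one costs almost nothing and may gain a little precision

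*Combined protocol and SAP*

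**What the plan says.** All of this is in the combined protocol and SAP.

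- **Primary Outcomes, MANCOVA at post-assessment.** MLQ presence and DASS-21 are analysed jointly, "with baseline presence sum score and baseline DASS-21 sum score as covariate and condition" as the between-subjects factor. Both outcomes are therefore adjusted for both baselines.
- **Primary Outcomes, ANCOVA for meaning in life at post-assessment.** The model has "post-assessment sum score of presence subscale of the MLQ as dependent variable and baseline presence sum score as" the covariate. Baseline DASS-21 is not in it.
- **Primary Outcomes, ANCOVA for internalizing symptoms at post-assessment.** The model is an "ANCOVA with post-assessment DASS-21 sum score as dependent variable and baseline DASS-21 sum score as covariate". Baseline MLQ presence is not in it.
- **Primary Outcomes, follow-up.** Each ANCOVA is repeated on the follow-up score, adjusted for the baseline and the post-assessment score. These models already have two covariates.
- **Statistical Analyses, sample size.** N = 128 rests on "testing a one-way ANCOVA with α -level of .05", f = 0.25, two groups, numerator df of 1 and "max. number of covariates = 2".
- **Procedure.** Both scales belong to the baseline battery, and randomisation follows its completion. Allocation is by simple randomisation.

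The plan gives no reason for the two covariate sets, no correlations between the scales, and no list of predictors for the imputation model.

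**The concern.** The outcome-specific ANCOVAs are the analyses that speak to H1a and H1b separately. At post-assessment each leaves out a pre-randomisation score that the joint model for the same outcomes includes. Three things follow.

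1. **Precision.** If the other baseline predicts the outcome beyond the own baseline, leaving it out keeps avoidable residual variance and leaves chance imbalance in that score uncorrected. Simple randomisation does not control such imbalance.
2. **Consistency.** A MANCOVA fits the same regression to each outcome. Its per-outcome condition coefficients are those of an ANCOVA with both baselines. The plan therefore contains two different adjusted condition effects for one outcome at one visit, and does not say which governs.
3. **Drop-out.** All analyses are on completers. If drop-out depends on the other baseline differently by arm, and that baseline predicts the outcome, the own-baseline estimate carries some bias that the two-baseline model does not.

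**Working it through.** **Inputs from the document:** alpha 0.05, f = 0.25, two groups, numerator df 1, up to two covariates, N = 128, drop-out 10%, recruitment target 142.

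**Assumed, because the document does not give them:** equal allocation; the partial correlation r of the other baseline with the outcome, given the own baseline; the drop-out model in step 5.

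**Step 1. Reproduce the plan's N.** Noncentral F test with λ = f² × N = 0.0625 × 128 = 8, df1 = 1, df2 = N − 2 − (number of covariates).

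| Covariates | df2 | Power at N = 128 |
|---|---|---|
| 1 | 125 | 0.8014 |
| 2 | 124 | 0.8014 |
| 3 | 123 | 0.8013 |

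The required N is 128 in all three cases, so the plan's figure reproduces. Recruitment: 128 / 0.9 = 142.2, which agrees with 142 apart from rounding up to 143.

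**Step 2. Cost in degrees of freedom.** Going from one covariate to two changes power by less than 0.01 percentage points.

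**Step 3. Power gain.** Take f = 0.25 as the effect size with the own baseline only. Adding the other baseline multiplies residual variance by 1 − r², so f becomes 0.25 / √(1 − r²) and λ becomes 8 / (1 − r²), with df2 = 124.

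| r | λ | Power at N = 128 | N for 80% power |
|---|---|---|---|
| 0 | 8.000 | 0.801 | 128 |
| 0.1 | 8.081 | 0.805 | 127 |
| 0.2 | 8.333 | 0.817 | 123 |
| 0.3 | 8.791 | 0.837 | 117 |

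**Step 4. Standard error, net of the lost df and of chance imbalance in the added covariate.** The expected variance ratio, two baselines against one, is (1 − r²) × (N − 4)/(N − 5) = (1 − r²) × 124/123.

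- r = 0: √(124/123) = 1.0041, so the SE rises by 0.4%.
- r = 0.1: √(0.99 × 124/123) = 0.9990, a fall of 0.1%.
- r = 0.2: √(0.96 × 124/123) = 0.9838, a fall of 1.6%.
- r = 0.3: √(0.91 × 124/123) = 0.9578, a fall of 4.2%.
- Break-even: r² = 1/124, so r = 0.09.

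The powers in step 3 charge for the lost degree of freedom but not for chance imbalance. Dividing 8 by the variance ratio instead gives 0.798, 0.802, 0.814 and 0.834 for r = 0, 0.1, 0.2 and 0.3, about 0.3 points lower in each row.

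**Step 5. Illustrative drop-out bias, by large-sample simulation.** The baselines correlate −0.4 and the own-baseline slope is 0.6. Drop-out in the intervention arm is logistic in the other baseline, with a log-odds slope of 0.5 to 1 per SD. Waitlist drop-out has the same overall rate but is unrelated to that baseline. With r from 0.1 to 0.3 and no true effect, the absolute bias in residual SD units is:

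| Drop-out | Own baseline only | Both baselines |
|---|---|---|
| 10% | 0.005 to 0.025 | under 0.002 |
| 20% | 0.01 to 0.05 | under 0.003 |

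The two-baseline values are within simulation error of zero. The effect assumed in the sample size is 2 × 0.25 = 0.5 SD.

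**The case against.** An ANCOVA adjusted for its own baseline is conventional and unbiased under randomisation. A standard MANCOVA has to use one covariate set for all outcomes, so there is a structural reason why both baselines appear there and not in the separate models. The two-baseline fit is also already in the plan, inside the MANCOVA. All of this stands, and it is why the point is a refinement. What it leaves open is that the plan neither promises to report the per-outcome MANCOVA estimates nor says which estimate governs.

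Stronger readings are tempting, but the document does not support them:

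- **That every primary ANCOVA uses only its own baseline.** This is true of the two post-assessment models. The two follow-up models add the post-assessment score, so the two-covariate allowance is already used there. The other baseline would be a third covariate.
- **That the precision is free.** The gain depends on a correlation that the document does not give, and below about 0.09 there is a slight loss. The invariant causal prediction section does not settle this. It is exploratory, works on change scores, and looks at a link through intolerance of uncertainty. That is not evidence that one scale's baseline predicts the other outcome after own-baseline adjustment. The plan also does not say whether f = 0.25 was meant after one covariate or two.
- **That adding the baseline removes drop-out bias.** It does so only for drop-out that depends on that baseline, differs by arm, and depends on nothing else relevant. If the predictive mean matching model includes the other baseline, part of the protection may already be there for any values that are imputed.

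**Conclusion.** The point holds for the two post-assessment primary ANCOVAs as a small improvement in efficiency and consistency. The planned models are valid.

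The cost is certain and negligible: power stays at 0.801 by the plan's own formula, and the SE rises by at most about 0.4% if the other baseline is uninformative. The gain is conditional: from nothing to about 3.5 power points for an assumed partial correlation between 0 and 0.3, taking f = 0.25 as the own-baseline effect size.

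Agreement between the ANCOVA and the per-outcome MANCOVA estimates does not depend on that correlation. It requires only that both are fitted to the same participants and the same imputed values.

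The drop-out benefit is minor. At the plan's 10% drop-out, 0.005 to 0.025 SD is 1% to 5% of the assumed 0.5 SD effect, under assumed slopes, and the wider limitations of a completer analysis remain.

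**What to change.** In the Primary Outcomes section, state that both post-assessment primary ANCOVAs (MLQ presence and DASS-21) use baseline MLQ presence and baseline DASS-21 as covariates, as the MANCOVA at that visit does. Settle this before outcomes are analysed, so that the covariate set cannot be chosen after seeing results.

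The cost is one sentence. It needs no new data, no change to N = 128 or to the recruitment target, and it stays within the two covariates allowed.

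The follow-up ANCOVAs are outside this change. They already use two covariates and condition on a score measured after randomisation, so their covariates should be considered and stated separately.
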